Consenting and Screening Evaluation. Parents and adolescent will be approached about participating in the study after review of their medical charts upon admission to the Bradley, Butler, or Hasbro. Study staff will obtain consent. All research staff will be trained in the steps necessary to obtain consent. All participants and their parents will be fully informed about the purpose and procedures of the study both verbally and through a written description contained in the assent/consent forms. All participants will be required to provide assent and their parents/guardians to sign an informed consent document in order to participate in the study.

Once consented, participants will be assessed for a suicide attempt prior to index psychiatric admission using the C-SSRS. Next participants will be screened for current psychosis and cognitive disability using the K-SADS-PL and the WASI, respectively, and complete the screening form. Those meeting all eligibility criteria will complete the PROMIS and Connors-3, which will be included as covariates in analyses. Eligible participants will also be asked about their current medication use, and the information they provide will be confirmed with a parent.

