After completing these assessments, participants will be randomly assigned to receive either anodal tDCS to rIFG, anodal tDCS to IOFC, or sham stimulation. tDCS at a constant current of 1.5 mA and sham stimulation will be applied for one 20-minute session. In the sham condition, the current will be ramped up to 1.5mA for 30 seconds and then ramped back down to 0. As this commonly used sham procedure produces a brief tingling sensation, participants are kept unaware of their experimental condition. Prior to and tDCS, participants will complete the SST and TCIP, while EEG is recorded to extract ERPs in a single-blind procedure. The participants and PI [name] will be blind to experimental condition, but Co-I [name] will not be blinded. Resting-state EEG, for 5 minutes, will be recorded before pre-stimulation tasks and after post-stimulation tasks. These tasks were specifically chosen because they can be administered well within an hour, the approximate duration of effect from a single-session of tDCS. The side effects questionnaire will be administered following the tDCS session. Ordering of tasks will be counterbalanced. These assessments will take about 3.5 hours total and they will be audio recorded for supervision and training purposes with participants' permission. They will take place in an interview room in the hospital, outside of any clinical care. Adolescent participants and parents will be paid \$100 and \$25, respectively, upon completion of the study.

Assessment Measures.

i. Self-report measures

Wechsler Abbreviated Scale of Intelligence (WASI; Wechsler, 1999): The WASI uses vocabulary, similarities, block design, and matrix reasoning subtests similar to those of the WAIS to provide an estimate of full scale IQ in approximately 30 minutes.

Depressive symptoms will be assessed using the pediatric version of the PROMIS depression scale. Higher scores reflect greater symptom severity.

The Conners-3 Self-Report (Conners-3 SR; Kollins, Epstein, & Conners, 2004): Current ADHD symptoms will be assessed with the Conners-3, with higher scores reflecting greater severity. ADHD will be a covariate in all analyses, as impulsivity is a hallmark of this disorder.

Suicidal ideation will be measured using the Passive and Active Suicidal Ideation Scale (PASIS). Higher scores reflect greater severity of ideation.

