Two Choice Impulsivity Paradigm (TCIP; Dougherty et al., 2003): The TCIP will be used as a delay discounting task (DDT) to assess impulsive choice, which requires participants to choose between immediate but small rewards and delayed but larger rewards over 50 trials. Delay discounting (or impulsive choice), is the tendency to undervalue an anticipated future reward as the time delay to obtaining the reward increases. A higher discounting rate (i.e., preference for smaller immediate rewards over larger delayed rewards) is viewed as reflecting greater cognitive impulsivity.

Stop-Signal Task (SST; Hamilton et al., 2015): The SST will be used to assess behavioral impulsivity. The SST requires participants to respond to a target stimulus as quickly and accurately as possible by pressing a button, but also to withhold their response when they hear an auditory signal. Thus, this task involves a competition between activating and inhibiting processes.

iv. **tDCS and EEG.** tDCS will be applied and EEG recordings made using a starstim/enobio device, with stimulation and recording electrodes located inside the cap. This device provides the user with up to 8 stimulating electrodes that can be programmed through software to be either anodal or cathodal in polarity and up to 32 recording electrodes. When not being used for stimulation, the 8 stimulating electrodes can also be used for recording, allowing for a total of 40 electrodes to be used for recording EEG pre- and post-stimulation. As in past studies, electrodes will be placed according to standard 10-10 coordinates corresponding to the rIFG (anode over F8 and cathode over FP1), which has been associated with behavioral impulsivity, and the IOFC (anode over FP1 and cathode over FP2), which has been linked with cognitive impulsivity.

Data analysis

Aim	Hypothesis	Dependent	Independent†	Analysis	MDE‡
1	H1	SST	tDCS/rIFG, time, tDCS/rIFG×time	GLM (repeated-measures ANOVA)	d=0.35
2	H2	SST	As above, plus reduced theta power (EEG), increased P3 (ERP)	As above with effects for EEG and ERP added; change in tDCS parameter estimate informs mediation	r=0.35
EA	EH1	DDT	tDCS/IOFC, time, tDCS/IOFC×time	GLM (repeated-measures ANOVA)	d=0.35
	EH2	DDT	As above, plus reduced VLFO (EEG), reduced SCPs (ERP)	As above with effects for EEG and ERP added; change in tDCS	r=0.35

† All analyses will include PROMIS (depressive symptoms) and Connor-3 (ADHD symptoms) as covariates

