‡ MDE minimal detectable effect, expressed as standardized mean difference (Cohen's d) for aim 1 and minimal detectable correlation for aim 2 (n=60), assuming type-I error level 5% and type-II error level 20%. Repeated-measures ANOVA assumes correlation of 0.9 of repeated measures.

Protection of Human Subjects

Source of Research Material

Adolescents will complete interviews, self-report measures, computer tasks, EEG testing, and tDCS. The data will be obtained for research purposes.

Recruitment and Consent

Parents and adolescents will be contacted about participating in the study after their medical records have been reviewed upon admission to Bradley, Butler or Hasbro. Medical charts will be reviewed by trained members of the research team familiar with the study criteria. These study staff will coordinate with treatment providers to arrange times to meet with potentially eligible patients and their parents in person. The staff will present and explain the study to the adolescent patient and his or her parent at Bradley, answer any questions they may have, and, if appropriate, present and explain the consent forms. All patients and parents will be fully informed of the purposes and procedures of the study. PI [name] will train the research staff in the steps necessary to obtain consent. All participants and parents will be fully informed about the purpose and procedures of the study both verbally and through a written description contained in the assent/consent forms. PI [name] and other study staff will be responsible for soliciting and obtaining informed consent/assent after any questions have been addressed. All participants will be required to provide assent and their parents or guardians to sign an informed consent document in order to participate in the study. Patients will be provided with a copy of the consent document, and the original will be placed in the PHI filing cabinet.

Potential Risk

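### Test H1 and EH1 by ANCOVA on the baseline task score: group×time is a change-score test that the two planned covariates may not touch, and its d=0.35 rests on an unsourced correlation and an unnamed contrast

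*Combined protocol and SAP*

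**What the plan says.** The Data analysis table lists the H1 terms as "tDCS/rIFG, time, tDCS/rIFG×time", fitted by a GLM described as repeated-measures ANOVA. EH1 has the same structure with the lOFC term. Both rows give an MDE of d=0.35. Footnote ‡ sets 5% type I and 20% type II error, does not say whether the test is one- or two-sided, and adds: "Repeated-measures ANOVA assumes correlation of 0.9 of repeated measures". No source or pilot value is given for that correlation.

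Footnote † states: "All analyses will include PROMIS (depressive symptoms) and Connor-3 (ADHD symptoms) as covariates". The Assessment Measures section gives the reason for one of them: "ADHD will be a covariate in all analyses, as impulsivity is a hallmark of this disorder". Both are collected at screening, before randomisation: "Those meeting all eligibility criteria will complete the PROMIS and Connors-3, which will be included as covariates in analyses". No repeat is planned.

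There are three arms of 20: "participants will be randomly assigned to receive either anodal tDCS to rIFG, anodal tDCS to IOFC, or sham stimulation". Both tasks are given before and after stimulation, so each participant has a baseline task score. The table does not name the comparator for the rIFG or lOFC term, or say which model term is the test.

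**The concern.** I take group×time to be the tested term. The group main effect would have a much larger MDE at r=0.9 (0.76 for 20 v 40, 0.89 for 20 v 20), which does not fit 0.35. Three things then follow.

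1. A covariate that is constant over the two occasions and enters only as a main effect drops out of group×time when pre/post pairs are complete. It acts on the test only through covariate×time terms, on which the plan is silent. Two analysts could both follow the text and report different primary estimates, and the stated reason for adjusting for ADHD symptoms might not be met.
2. The baseline task score is collected but not used as a covariate. A change score fixes its coefficient at 1, which costs precision when the pre-post correlation is below 0.9. A chance baseline imbalance also carries over into the estimate by (1−r) times its size.
3. The 0.35 is the only sensitivity stated for H1 and EH1. It depends heavily on r, and it cannot be tied to a contrast because comparator and sidedness are missing.

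**Working it through.** **Inputs.** From the documents: 20 per arm, three arms, 5% type I error, 80% power, r=0.9. Assumed: equal variance at the two occasions (SD=1), no dropout, PROMIS and Conners-3 explaining nothing beyond baseline, and all values of r other than 0.9.

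**Formulas.** MDE = λ × √[V × c × (1/n₁ + 1/n₂)].
- λ is the noncentrality giving 80% power on the noncentral t with N−2−k df, for k covariates.
- V = 2(1−r) for a change score and 1−r² for ANCOVA.
- c = (N−3)/(N−3−k) allows for estimating the covariate slopes.

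**Reproducing 0.35 at r=0.9.** V = 2(0.1) = 0.2 and k=0.
- 20 v 40, two-sided: λ=2.849 and √(0.2×0.075)=0.1225, giving **0.349**.
- 20 v 20, two-sided: λ=2.875 and √(0.2×0.1)=0.1414, giving **0.407**.
- 20 v 20, one-sided: λ=2.532 and the same 0.1414, giving **0.358**.

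So 0.35 fits one active arm against the other two pooled, which mixes sham with the other active site, and nearly fits a one-sided comparison with sham. For two-sided active v sham, power at d=0.35 is 67%.

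**ANCOVA with three covariates at r=0.9.** V = 1−0.81 = 0.19.
- 20 v 20: c=37/34=1.088 and λ=2.881, giving 2.881×√(0.19×1.088×0.1)=0.414.
- 20 v 40: c=57/54=1.056 and λ=2.852, giving 2.852×√(0.19×1.056×0.075)=0.350.

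**Two-sided MDE over r.** The adjusted change score is what results if covariate×time terms are fitted.

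| r | 20 v 20: change, unadjusted | change, adjusted | ANCOVA | 20 v 40: change, unadjusted | change, adjusted | ANCOVA |
|---|---|---|---|---|---|---|
| 0.95 | 0.287 | 0.296 | 0.297 | 0.247 | 0.251 | 0.251 |
| 0.9 | 0.407 | 0.419 | 0.414 | 0.349 | 0.355 | 0.350 |
| 0.8 | 0.575 | 0.592 | 0.570 | 0.493 | 0.503 | 0.481 |
| 0.7 | 0.704 | 0.725 | 0.679 | 0.604 | 0.616 | 0.573 |
| 0.5 | 0.909 | 0.936 | 0.823 | 0.780 | 0.795 | 0.695 |

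ANCOVA overtakes the unadjusted change score once r falls below about 0.83 (20 v 20) or 0.89 (20 v 40). Against the adjusted change score the crossing points are 0.940 and 0.962. A simulation of 20,000 trials per cell agrees: at r=0.7, 20 v 20, the variance ratio of ANCOVA to adjusted change score was 0.881.

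**Whether the covariates act.** In a simulated 60-participant data set, with one of two covariates related to the outcome, group×time was 0.2292 (SE 0.1263) both without covariates and with both entered as main effects. With covariate×time terms it moved to 0.2539 (SE 0.1231). In 200 further data sets without those terms, the estimate equalled the raw difference in mean change to within 5×10⁻¹⁵.

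**Baseline imbalance.** One standard error at 20 v 20 is √(1/20+1/20)=0.316 SD. The change-score estimate shifts by (1−r)×0.316: 0.03 SD at r=0.9, 0.09 at 0.7 and 0.16 at 0.5. ANCOVA removes the linear part of this with an estimated slope.

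**The case against.** The planned test is valid under randomisation, and the study's stated interest is in change. At r=0.9, the only correlation the documents give, ANCOVA buys nothing: it is marginally worse than the unadjusted change score (0.414 v 0.407; 0.350 v 0.349). Its small advantage at r=0.9 appears only against a change score already adjusted for PROMIS and Conners-3, and that analysis would itself remove the covariate ambiguity. One sentence committing to covariate×time terms would also remove it without a change of model. On this view the main gap is the unnamed comparator and sidedness, and ANCOVA is a preference.

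Most of this stands as a limit on the point. There is no bias to correct, no gain at the planning value, and the lower correlations are assumed. Naming the contrast and giving a source for r arguably matter more than the model switch, and ANCOVA does not restore d=0.35 if r is well below 0.9. But none of this makes the switch wrong. It settles the covariate question without relying on a software default, and it limits the loss if the unsourced 0.9 is too high. At r=0.9 its cost in MDE is under 0.01 SD.

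**Conclusion.** The concern holds as a recommended improvement, with medium confidence. As written, the model does not establish that PROMIS and Conners-3 act on the tested effect. That conclusion rests on reading group×time as the test and on complete pre/post pairs. The stated 0.35 cannot be assigned to one contrast: two-sided, it matches 20 v 40 (0.349) and not active v sham (0.407).

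The precision benefit of ANCOVA depends on r. It is absent at 0.9. Against the unadjusted change score at 20 v 20 it is 0.025 SD at r=0.7 (0.704 to 0.679) and 0.086 SD at r=0.5 (0.909 to 0.823). Those correlations are assumptions, as are equal variances, no dropout and covariates that add nothing beyond baseline.

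**What to change.** **Primary change.** For H1 and EH1, make the primary model an ANCOVA of the post-stimulation task score on arm, baseline task score, PROMIS and Conners-3.

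**Alongside it.** Name the comparator, the sidedness and the tested term. Restate the MDE for that contrast over r=0.5 to 0.95, with a source for the planning value. If the comparator is the other two arms pooled, say that it combines sham with the other active site. If repeated-measures ANOVA is kept, state that group×time is the test and whether covariate×time terms are fitted. For H2 and EH2, use the same outcome and baseline task score so that the arm estimates being compared come from matching models; this is for consistency, and no gain was computed there.

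**Cost.** New wording in two table rows and the footnote, and no new data. ANCOVA uses one more degree of freedom than the adjusted change score and three more than the unadjusted one. At r=0.9 its MDE is therefore larger than the unadjusted one by 0.007 (20 v 20) or 0.001 (20 v 40). That is recovered if PROMIS and Conners-3 together explain about 3.7% (1−(0.4066/0.4143)²) or 0.5% (1−(0.3489/0.3497)²) of the post-score variance left after baseline, a quantity the documents do not give. H2 and EH2 gain one term, or at least three if pre-stimulation EEG and ERP values are also added. The restated MDE may look less favourable than 0.35.
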